6.2.3.2 Pregnancy Tests

A pregnancy test will be performed for all women of childbearing potential according to the schedule in Appendix 1. A negative serum pregnancy test performed at Screening must be confirmed along with a negative urine pregnancy test on Day 1 prior to randomization and dispensing/administration of study drug.

6.2.3.3 Adverse Events

The Investigator is responsible for the detection and documentation of events that meet the definition of an AE or SAE as provided in this protocol. Assessments of occurrences of AEs or SAEs should be conducted during each study visit or as reported by the subject outside of

scheduled visits. To fulfill safety reporting obligations, the Investigator should include in his or her assessment any AEs resulting from study participation regardless of relation to study drug (e.g., complications resulting from the taking of a blood sample).

6.2.3.4 Vital Signs

Vital signs will include blood pressure (systolic and diastolic in mm Hg), heart rate (beats per minute), body temperature, and O₂ saturation. Vital sign measurements will be collected at every visit. Subjects should be seated for 5 minutes prior to assessment of vital signs. Blood pressure measurements should be measured on the same arm throughout the study.

6.2.3.5 Electrocardiogram (ECG)

A 12-lead ECG (Supine) will be performed on all subjects using a standard ECG machine at Visit 1, (Screening), Visit 2 (Baseline), Visit 5 (Day 29/EOT/ET), and Visit 9 (Day 43/EOS), if applicable.

6.2.3.6 Physical Examination

A full physical examination will be performed at Visit 1 (Screening). Symptom-directed physical examinations will be performed at other visits. Weight will be collected as outlined in [Appendix 1](#). Height will only be collected at Visit 1 (Screening).

6.3 Other Assessments

6.3.1 Assessment of VOCs

VOCs that subjects experience during the study will be collected. A VOC is defined as:

- The occurrence of appropriate symptoms consistent with a painful crisis, acute chest syndrome (ACS), or priapism, and
- Requires visit to a medical facility, and
- Receipt of either a parenteral or oral opioid or NSAID analgesia.

For each VOC, the information outlined in [Section 7.3](#) will be collected.

6.3.2 Medical History

Each subject's complete medical history is to be recorded in source documents and the appropriate eCRF pages. Relevant medical history will be collected for the 3 months prior to the Screening Visit. A detailed history of the subject's VOCs over the past 12 months will be obtained and will include the start and stop dates (if known), the treatment setting, and treatment including drug, dose, route of administration, and duration of treatment for each VOC, when possible.

7.0 SAFETY REPORTING

7.1 Operating Definitions for Assessing Safety

Safety data collection for this study begins at the time of the subject's signing of the informed consent according to the operating definitions defined in this section of the protocol. The Investigator is responsible for the detection and documentation of events that meet the definition of an AE ([Section 7.1.1](#)), or SAE ([Section 7.1.2](#)).

7.1.1 Adverse Event

An adverse event is any untoward medical occurrence in a clinical investigation subject administered a study product and which does not necessarily have to have a causal relationship with this treatment.

An AE can therefore be any unfavorable and unintended sign (that could include a clinically significant abnormal laboratory finding), symptom, or disease temporally associated with the use of a study product, without any judgment about causality (i.e., whether or not considered related to the study product).

An AE does include the following:

- Exacerbation or worsening of a pre-existing illness including symptoms associated with SCD.
- Condition detected or diagnosed after study product administration even though it may have been present prior to the start of the study.

An AE does not include the following:

- Medical or surgical procedures (e.g., surgery, endoscopy, tooth extraction, transfusion) as event terms; the condition that led to the procedure is the AE if it meets the definition of an AE.
- Situations where an untoward medical occurrence has not occurred (e.g., hospitalization for cosmetic elective surgery; and social and/or convenience admissions).
- Symptoms associated with disease, which are consistent with the subject's usual clinical course; unless the subject experiences worsening of their symptom(s) or the symptom(s) meet the criteria for an SAE (exception is VOC and presenting symptoms, [Section 7.3](#)).

7.1.2 Serious Adverse Event

A serious adverse event is any untoward medical occurrence that, at any dose:

- Results in death,

- Is life-threatening.

NOTE: The term “life-threatening” in the definition of “serious” refers to an event in which the subject was, in the view of the Investigator or Sponsor, at risk of death at the time of the event. It does not refer to an event which hypothetically might have caused death if it were more severe.

- Requires inpatient hospitalization or prolongation of existing hospitalization.

NOTE: Complications that occur during hospitalization are AEs. If a complication prolongs hospitalization or fulfills any other serious criteria, the event is serious. Hospitalization for elective treatment of a pre-existing condition that did not worsen from Baseline is not considered to be an AE. “In-patient” hospitalization means the subject has been formally admitted to a hospital for medical reasons for 24 hours or more. It does not include presentation at a casualty or emergency room.

- Results in a persistent or significant incapacity or substantial disruption of the ability to conduct normal life functions.

NOTE: The term disability means a substantial disruption of a person’s ability to conduct normal life functions. This definition is not intended to include experiences of relatively minor medical significance such as uncomplicated headache, nausea, vomiting, diarrhea, influenza, or accidental trauma (e.g., sprained ankle) that may interfere or prevent everyday life functions but do not constitute a substantial disruption.

- Is a congenital anomaly or birth defect in the offspring of a subject who received study product.

Important medical events that do not result in death, are not life-threatening, and/or do not require hospitalization may be considered an SAE when, based upon appropriate medical judgment, they may jeopardize the subject or may require medical or surgical intervention to prevent one of the outcomes listed in this definition.

NOTE: Examples of such medical events include allergic bronchospasm requiring intensive treatment in an emergency room or at home, blood dyscrasias or convulsions that do not result in inpatient hospitalization, or the development of drug dependency or drug abuse.

Additionally, an adverse event meeting any of the serious outcomes previously defined above that is assessed by the Investigator as resulting from study participation (regardless of relationship to study drug) should be treated as an SAE for this protocol (e.g., complications resulting from the taking of a blood sample or performance of a protocol required procedure).

Medical and scientific judgment should be exercised in deciding whether expedited reporting is appropriate in case of events that do not meet the serious criteria.

If a subject has an SAE, a plasma sample for PK analysis will be collected as soon as feasible, and the date and time of the last 2 rifaximin doses will be recorded.

7.2 Clinical Laboratory Abnormalities and Other Abnormal Assessments as AEs and SAEs

Abnormal laboratory findings (e.g., clinical chemistry, hematology) or other abnormal assessments (e.g., abnormal findings during examinations, the taking of vital signs, or ECG monitoring) that are judged by the Investigator as clinically significant must be recorded as AEs or SAEs if they meet the definition of an AE or SAE. The Investigator should exercise his or her medical and scientific judgment in deciding whether an abnormal laboratory finding or other abnormal assessment (including ECG monitoring) is clinically significant. Abnormal laboratory findings consistent with pre-existing illness or confirmatory of a reported AE or SAE should not be reported as a separate AE or SAE. If a clinically significant change from Baseline is observed which is indicative of worsening in condition, then the worsening condition should be reported as the AE or SAE.

7.3 Adverse Events That Are VOC Endpoint Events

VOC events that are listed in [Table 3](#) are being captured as endpoints and **SHOULD NOT** be reported as an AE or SAE for purposes of this study. These events will not be considered as SAEs for reporting requirements.

Table 3: VOC Events Not Requiring AE/SAE Reporting

Uncomplicated pain crisis*
Acute chest syndrome
Hepatic sequestration
Splenic sequestration
Priapism requiring a visit to a medical facility

* Defined as the occurrence of appropriate symptoms, results in a visit to a medical facility and/or healthcare professional and requires either parenteral or oral opioid or NSAID analgesia, but is NOT classified as an acute chest syndrome, hepatic sequestration, splenic sequestration, or priapism.

All VOCs are to be recorded only once on the “Vaso-Occlusive Event” eCRF page. All VOCs are to be recorded throughout the entire treatment period, up to Visit 5 (Day 29), and should continue until the Follow-Up Visit at Day 43. The Investigator will classify and provide all the following information for each VOC as follows:

- Diagnosis, which will be limited to one of the five pre-defined VOC events as:
 - Uncomplicated pain crisis
 - ACS

- Hepatic sequestration
- Splenic sequestration
- Priapism (requiring a visit to a medical facility)
- Onset date,
- Stop date,
- Action taken (None, Required concomitant medication, Temporarily withheld study drug, Permanent discontinuation of study drug, or Other [explain]),
- Treatment setting,
- Concomitant medications given, and
- Outcome (Recovered without sequelae, Resolved with sequelae, Ongoing, Unknown, Death).

If a subject is hospitalized due to a VOC and during hospitalization develops a non-VOC event that meets the criteria for a SAE, then that event should be reported as a SAE. Any prolongation of a hospitalization due to a non-VOC event (even though they may have initially been hospitalized due to a VOC) is reportable as a SAE in the eCRF.

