2.2.3 Exploratory Assessments

Information on any potential VOCs experienced during the study will be collected as follows:

- Dates and duration of each episode. A VOC is defined as:
 - The occurrence of appropriate symptoms consistent with a painful crisis, acute chest syndrome (ACS), or priapism, and
 - Requires visit to a medical facility, and
 - Receipt of either a parenteral or oral opioid or NSAID analgesia.
- Categorization of VOCs. Subcategories will consist of:
 - Uncomplicated pain crisis, defined as a painful crisis that is NOT classified as an acute chest syndrome, hepatic sequestration, splenic sequestration, or priapism.
 - Acute Chest Syndrome (ACS), defined as a finding of a new pulmonary infiltrate involving at least one complete lung segment that was consistent with alveolar consolidation, but excluding atelectasis (as indicated by chest X-ray). Must also present with at least one of the following signs or symptoms: patient-reported chest pain, body temperature of more than 38.5 °C, tachypnea, wheezing, or cough.
 - Hepatic sequestration, defined as findings of right upper quadrant pain, an enlarged liver, and an acute decrease in hemoglobin concentration.
 - Splenic sequestration, defined as findings of left upper quadrant pain, an enlarged spleen, and an acute decrease in hemoglobin concentration.
 - Priapism, defined as having a sustained penile erection requiring a visit to a medical facility.

- Intravenous opioid analgesia (IOA) and oral opioid use during VOCs, including date/time of each start and stop of treatment, dose, drug, inpatient/outpatient setting, and date/time of readiness-to-discharge.

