4.0 SELECTION AND WITHDRAWAL OF SUBJECTS

4.1 Inclusion Criteria

A subject will be eligible for inclusion in this study if he/she meets all of the following criteria:

1. Subject must have the ability and willingness to sign a written informed consent form.
2. Subject is between the ages of 18 to 70 years old (inclusive) at the time of consent.
3. Subject has SCD of any genotype (HbSS, HbSC, HbS β-thalassemia). If the subject's genotype has not been previously documented, genotyping will be performed during Screening using high-performance liquid chromatography (HPLC)/electrophoresis.
4. Subject must have experienced at least 2 VOCs within the 12 months prior to Screening.
A VOC is defined as:
 - a. The occurrence of appropriate symptoms consistent with a painful crisis, acute chest syndrome (ACS), or priapism, and
 - b. Requires a visit to a medical facility and/or healthcare professional, and
 - c. Receipt of either a parenteral or oral opioid or NSAID analgesia.
5. If subject is receiving hydroxyurea (HU)/hydroxycarbamide (HC), subject must have been receiving the treatment for at least 6 months prior to Screening and must agree to maintain the same dose and schedule for the duration of the study.
6. Subjects must have laboratory values at Screening within the following ranges:
 - Absolute Neutrophil Count $\geq 1.0 \times 10^9/L$
 - Platelets $\geq 75 \times 10^9/L$
 - Hemoglobin (Hgb) $\geq 6.0 \text{ g/dL}$
 - Glomerular filtration rate (GFR) $\geq 45 \text{ mL/min}/1.73 \text{ m}^2$ using the CKD-EPI formula
Total bilirubin $\leq 15 \text{ mg/dL}$
 - Alanine transaminase (ALT) $\leq 3.0 \times \text{ULN}$
 - International Normalized Ratio (INR) ≤ 2.0
7. Eastern Cooperative Oncology Group (ECOG) performance status ≤ 2 .
8. Women of child-bearing potential, defined as all women physiologically capable of becoming pregnant, must have a negative serum pregnancy test at Screening and agree to use standard prevention methods for the duration of the study.

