6.1.9 Visit to a Medical Facility for a VOC Event

The following assessments are to be completed, when possible, when a subject visits a medical facility for treatment of a VOC:

- Collect any adverse events since previous visit. Do not record VOC events as an AE (See [Section 7.3](#)).
- Collect concomitant medication changes since previous visit. Specifically collect opioid use.
- Obtain vital sign measurements (BP, HR, body temperature, and O₂ saturation).
- Conduct symptom-directed physical exam.
- Collect blood samples for hematology and blood chemistry and urine for urinalysis.
- Collect blood samples for CANs, CD62L, iFABP and LPS.
- Collect PK blood samples.
- Collect urine sample for 3-indoxyl sulfate.

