- b. Medical history will be obtained from prior 3 months. Detailed history of VOCs occurring over the past 12 months will be obtained. This will include collection of treatments for VOCs including drug, dose, route of admin, duration of treatment, and inpatient/outpatient setting.
- c. Vital signs will be obtained after the subject has been in a supine position for a minimum of 5 minutes. Vital signs include systolic and diastolic blood pressure, heart rate, body temperature, and oxygen saturation.
- d. Perform a full physical examination at Screening and symptom-directed physical examination at subsequent visits.
- e. A 12-lead ECG (supine) will be performed. An ECG will be performed at the Day 43 (EOS) Visit only if abnormal findings were observed at the Day 29 (EOT/ET) Visit.
- f. Hemoglobin genotyping will be recorded if known. If unknown at Screening, hemoglobin genotyping will be performed using HPLC/electrophoresis.
- g. Serum pregnancy test is to be performed at Screening for all women of childbearing potential. A negative Screening serum pregnancy test and a negative urine pregnancy test must be confirmed before randomization. Subsequent pregnancy testing will be with urine pregnancy test.
- h. Information on whether a VOC requiring a visit to a medical facility occurred will be recorded. Medications received during the VOC visit will be recorded.
- i. Only weight will be collected.
- j. Hematology, chemistry, and/or urinalysis will only be collected at this visit if needed for follow-up or resolution of AEs/SAEs.
- k. Not all treatment groups will return study drug at Visit 3 and Visit 4.
- l. During Screening, record all opioid use for the prior 30 days. At each visit, record all opioid use since the previous visit.

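### Section 7.3 exempts more events from AE/SAE reporting than the on-study VOC definition counts, and it leaves a death attributed to a VOC without a stated 24-hour SAE report

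*Combined protocol and SAP*

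**What the plan says.** Section 7.3 states that the VOC events in Table 3 are captured as endpoints and are not to be reported as AEs or SAEs. It adds: "These events will not be considered as SAEs for reporting requirements". Table 3 has five rows: uncomplicated pain crisis, acute chest syndrome (ACS), hepatic sequestration, splenic sequestration, and priapism with a facility visit. The footnote defines the first row as an event with appropriate symptoms that "results in a visit to a medical facility and/or healthcare professional and requires either parenteral or oral opioid or NSAID analgesia" and does not belong to one of the other four rows.

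The on-study VOC definition, given in the synopsis, 2.2.3 and 6.3.1, has three joint conditions: symptoms of a painful crisis, ACS or priapism; a facility visit ("Requires visit to a medical facility, and"); and an opioid or NSAID. Appendix 1 footnote h also speaks of the facility only: "Information on whether a VOC requiring a visit to a medical facility occurred will be recorded". The wider footnote wording matches the VOC history definition in inclusion criterion 4: "Requires a visit to a medical facility and/or healthcare professional, and".

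On deaths, 7.3 makes death one of the outcome codes for a VOC. Section 7.1.1 names VOC as an exception, with reference to 7.3. Section 7.1.2 makes death a seriousness criterion. Section 7.8 requires death to be reported as the SAE term if its cause is not available within the 24-hour period. Section 8.4.6 plans a summary of TEAEs with fatal outcome and a listing of all deaths.

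**The concern.** An exemption for disease-related endpoint events is sound only if every exempt event is counted as an endpoint instead. Here the exempt set is wider than the counted set. An event in the gap can be barred from the AE page by 7.3 and also fail the VOC definition in 6.3.1. Safety is a stated objective and VOCs are an exploratory readout, so both summaries by arm are exposed.

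The second issue concerns a fatal VOC. An investigator working from 7.1.2 would send an SAE report within 24 hours. One working from 7.3 would complete the VOC page and send none.

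**Working it through.** **1. Exempt set against counted set.** The five Table 3 rows are compared with the three conditions of the on-study definition.

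| Table 3 event | Symptom named in definition? | Facility visit required in Table 3? | Opioid or NSAID required in Table 3? |
|---|---|---|---|
| Uncomplicated pain crisis | Yes | Wider: a healthcare professional is enough | Yes |
| ACS | Yes | No | No |
| Hepatic sequestration | No | No | No |
| Splenic sequestration | No | No | No |
| Priapism | Yes | Yes | No |

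Two of five rows are not named in the symptom condition. Three have no visit condition and one has a wider one. Four have no analgesia condition. No row carries all three conditions, so each can be met by an event that the definition does not count.

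The cases are not equally strong. The pain crisis is explicit, because the footnote itself admits a crisis seen only by a professional. The other rows depend on a literal reading. Section 2.2.3 lists them as VOC subcategories with their own definitions, and those definitions require no analgesia. A sequestration with pain, a facility visit and analgesia could pass as a painful crisis. ACS needs a chest X-ray under 2.2.3, so its missing visit condition probably matters little; its missing analgesia condition can matter.

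**2. Route of a death attributed to a VOC.**

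- 7.1.1 and 7.3 together: VOC page, outcome coded as death, no SAE report. The only return to SAE reporting in 7.3 is for a non-VOC event during a VOC hospitalization, or a prolongation due to one.
- 7.1.2: death is serious, with no VOC exception mentioned.
- 7.8: a death of unavailable cause is reported as an SAE in 24 hours. A death already attributed to ACS, say, has no such instruction.
- 8.4.6: an event that is not an AE cannot enter the fatal-TEAE summary or the SAE counts. It does enter the listing of all deaths.
- Other routes: 6.1.10 collects death data at unscheduled visits, and 7.8 asks for postmortem findings; neither sets a deadline. The 24-hour notice in 10.1 applies only to problems that are unexpected, possibly related and suggestive of greater risk, all three together.

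**3. Scale.** The plan gives no expected VOC count to reproduce. Inputs: 60 subjects, and 12 per active arm (3.2); combined placebo is 6 + 6 = 12; Day 1 to Day 43 is 42 days. The lower rate is 2 per year, from inclusion criterion 4: "Subject must have experienced at least 2 VOCs within the 12 months prior to Screening". The upper rate is 2.25 per 6 months, or 4.5 per year, the expected rate cited from the earlier rifaximin study in Section 1.2.

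Expected VOCs = subjects × yearly rate × 42/365.25.

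- At 2 per year: 60 × 2 × 42/365.25 = 13.8 in all; 12 × 2 × 42/365.25 = 2.76 per arm; one event is 1/2.76 = 36%.
- At 4.5 per year: 60 × 4.5 × 42/365.25 = 31.05 in all; 12 × 4.5 × 42/365.25 = 6.21 per arm; one event is 1/6.21 = 16%.

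The Poisson standard deviation of an arm's count is √2.76 = 1.7 to √6.21 = 2.5.

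**The case against.** The strongest reply is that 7.3 is the operative rule and is workable. All VOCs go once on one eCRF page, with the diagnosis limited to the five Table 3 events, and 6.3.1 refers to 7.3 for the data to collect. Setting and medications are recorded for each VOC, so one definition can be applied centrally before database lock. Section 2.2.3 collects widely ("Information on any potential VOCs experienced during the study will be collected as follows"). The synopsis allows a summary of facility visits that are not VOCs. Section 8.0 leaves detail to a SAP. The term medical facility is not defined, so the gap may be small.

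Much of this stands, and a reader who infers that gap events are certainly lost goes too far. What remains is that no text says which definition governs the count. The synopsis clause is optional and does not reach a crisis seen only by a professional. Reading Table 3 as confined to events that already meet the definition does not rescue the footnote, which supplies its own, wider definition.

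On deaths, the reply is that 7.3 is specific and 7.1.2 general, so a rule exists: the VOC page. That is correct. A reader might infer that the plan is silent on a fatal VOC, or that such a death goes unrecorded, and the documents support neither. The conflict with 7.1.2 and the contrast with 7.8 remain.

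A reader might also infer a biased comparison of prior-year with on-study VOCs, since criterion 4 uses the wider wording. No such analysis is planned; prior VOCs are only a baseline descriptor (8.4.3).

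**Conclusion.** Both parts hold in limited form. Followed as written, a professional-only pain crisis can be neither a TEAE nor a counted VOC. On a literal reading the same is true of ACS, sequestration or priapism without an opioid or NSAID. The frequency is unknown: the documents give no split of VOCs by setting or analgesia, so no share can be derived.

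One event is 16% to 36% of an arm's expected VOC count. This assumes that the two rates continue on study with no treatment effect and no dropout. The lower rate rests on the wider eligibility wording, and the earlier study's VOC definition is not given. One event is also within chance variation for an arm, and the VOC summaries are exploratory, descriptive and optional. This is therefore a consistency defect worth correcting, with no major effect on the trial's conclusions shown.

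A death attributed to a VOC has no stated 24-hour SAE report and is outside the fatal-TEAE summary. It is still coded on the VOC page and listed with all deaths. This part rests on the text alone and needs no assumption about rates.

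**What to change.** Reconcile the synopsis, 2.2.3, 6.3.1, Table 3 and its footnote, and Appendix 1 footnote h to one on-study VOC definition. State that the AE/SAE exemption covers only events that meet that definition and are recorded on the VOC eCRF page, and that any other event is assessed under 7.1.1 and 7.1.2 in the usual way. The exemption should not be replaced by a rule that every other event is an AE, because 7.1.1 excludes disease symptoms in the subject's usual course unless they worsen or meet SAE criteria.

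Reconcile 7.1.1, 7.1.2, 7.3, 7.8 and 8.4.6 so that one explicit reporting and tabulation rule covers a VOC with fatal outcome.

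The cost is wording in the protocol and SAP, eCRF guidance, and a few extra forms for sites.
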